A new class of Ca^{2+} channel stabilizers, Rycals®, were developed by [name] at Columbia University. Under normal physiological conditions, Calstabin1 binds and stabilizes the RyR1 closed state. Rycals function as Ca^{2+} channel stabilizers by restoring RyR1-Calstabin1 binding when it is deficient, thereby stabilizing the RyR1 closed state. To date, [name] laboratory has tested Rycals pre-clinically in at least 20 *RYR1*-RM patient muscle biopsies *in vitro*, including ten obtained during a previous clinical trial (NCT02362425). All untreated samples initially showed decreased RyR1-Calstabin1 binding (<10- 40% of healthy control muscle), which improved to 70-90% of control levels upon treatment with Rycals *ex vivo*. This work has demonstrated that Rycal treatment can restore RyR1-Calstabin1 binding and rescue leaky RyR1 channels in human biopsies *ex vivo*. In addition, a few muscle disease mouse models demonstrated that Rycal treatment improved muscle strength and muscle cell survival and may therefore offer a promising treatment for *RYR1*-RM (Andersson and Marks, 2010; Capogrosso et al. 2018; Wanig et al. 2015). S 48168 may also have benefit for malignant hyperthermia susceptibility, a condition allelic to *RYR1*-RM, by restoring the conformational integrity of mutant RyR1 channels. The lead Rycal, S 48168 (ARM210), has completed Phase I clinical studies in healthy volunteers. In those studies, S 48168 (ARM210) was safe and well tolerated in single and multiple dose studies and has now been tested in six (6) patients with *RYR1*-RM. This study continues to test S 48168 (ARM210) in a Phase I trial in *RYR1*-RM patients.

The objectives of this study are to explore the safety and tolerability, pharmacokinetics (PK), pharmacodynamics (PD)/target engagement (TE) of S 48168 (ARM210), as well as effects on muscle/motor function, and fatigue in adult *RYR1*-RM patients. The open-label study design consists of approximately 8-20 participants and two dose groups. The first three participants received 120 mg S 48168 (ARM210) daily for approximately 28 (not to exceed 30) days. Three participants have been enrolled in the second group and received 200 mg S 48168 (ARM210) daily for approximately 28 (not to exceed 30) days. The decision to escalate to a top dose of 200 mg daily was made by an independent Data and Safety Monitoring Board (DSMB) after

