For each participant, the study duration will be approximately 2 months from enrollment to completion. Overall there will be three visits to the NIH Clinical Center (NIH CC), Bethesda, MD; one prior to the first dose, one at the end of the dosing period, and one approximately two weeks after the cessation of S 48168 (ARM210). Study participants will be contacted by phone/ secured email approximately weekly for follow-up regarding AEs and can describe daily any symptoms in a participant diary. Follow-ups will also serve to encourage study compliance. The dosing interval will be approximately 28 days (not to exceed 30 days). The day 42 follow-up assessment will be conducted in-person and include safety labs, , and the full battery of exploratory efficacy assessments.

Participants local to the study site will have the option of completing all weekly AE assessments at the NIH.

Study Population:	This study will be conducted in adult (≥ 18 years) male and female RYR1 -RM affected individuals. Dropouts/withdrawals may be replaced.
Dosage, Dosage Form, Route, and Dose Regimen:	The first three participants were dosed with 120 mg S 48168 (ARM210) (6 x 20 mg tablets) daily for approximately 28 days (not to exceed 30 days). These participants will be provided an opportunity to re-enroll and receive the high dose. The second group was dosed with 200 mg S 48168 (ARM210) (10 x 20 mg tablets) daily for approximately 28 days (not to exceed 30 days). Study investigators will administer S 48168 (ARM210) during the time the participant is confined to the NIH CC for 24h PK assessments. Baseline (Day 0) 24hr PK assessments will not be conducted in participants who already received the low dose. Dosing was staggered for the first three participants at each dose level, starting each participant on drug after the previous participant had finished 14 days of dosing. Study investigators will instruct the

	
participant in the proper dosing instructions for home administration when drug supplies are dispensed.
 
Study drug (S 48168 [ARM210]) tablets will be provided to the participant in a bottle. All participants will be instructed to self-administer the study medication daily with water in the morning. Compliance will be assessed during each phone/e-mail contact. Compliance will be verified at in-person visits for residual pill counts and by a participant diary.

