12.10.7.4 Reporting

All AEs that occurred during this clinical study will be recorded on the AE CRF using a recognized medical term or diagnosis that accurately reflects the event. For each adverse event, the investigator will provide the onset date, end date, intensity, treatment required, outcome, seriousness, and action taken with the investigational drug. The PI or designee will review each event and assess its relationship to drug treatment (likely, probably, possibly, unlikely or unrelated). Each sign or symptom reported will be graded in accordance with CTCAE (version 5), and the date of onset, time of onset, and outcome of each event will be noted. To fulfil the regulatory requirements for expedited safety reporting, the sponsor evaluates whether a particular AE is "listed" (i.e. known side effect of the drug or not). Medical judgment should be used to determine the causal relationship of adverse event, considering all relevant factors, including pattern of reaction, temporal relationship, de-challenge or re-challenge, confounding factors such as concomitant medication, concomitant diseases and relevant history. Serious AEs that are considered related to S48168 will be considered a suspected unexpected serious adverse reaction (SUSAR). Assessment of causal relationship must also be recorded on the CRF. If an AE has not resolved at the end of the study reporting period it will be documented as ongoing on the corresponding CRF.

Prompt reporting of adverse events is the responsibility of the PI or designee. The reporting period for AEs is the period immediately following each study administration through 28 days after each dose. AEs must be followed until resolution or stabilization, the subject is lost to follow-up, even if this extends beyond the 28-day post-dosing reporting period (for the purpose of obtaining a stop date for the event).

If an AE has not resolved at the end of the study reporting period it will be documented as ongoing on the corresponding CRF.

Each AE will be reviewed with the medical monitor, [REDACTED] and discussed with the PI. AEs will be reported to the DSMB, regardless of PI classification for review.

The AE severity definitions of CTCAE version 5 will be used for rating the severity of all AEs (Grade 1-5).

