6.3 Adverse Events

All adverse events (AEs) reported during this clinical trial will be coded using the Medical Dictionary for Regulatory Activities (MedDRA[®]), Version 21.0.

All adverse events will be reviewed by the Medical Monitor and graded in accordance with CTCAE version 5

(https://ctep.cancer.gov/protocoldevelopment/electronic_applications/ctc.htm)

All AEs captured in the database will be listed in by-subject data listings including verbatim term, coded term, treatment, severity, relationship to study medication, and action; however, only treatment-emergent AEs (TEAEs) will be summarized.

A TEAE is defined as an AE that is starting or worsening at the time of or after study drug administration. Each TEAE will be attributed to a treatment based on the onset date and time of the AE.

An AE will also be considered treatment emergent if: onset date of an AE is missing; if onset time of an AE is missing and the onset date is the same as the treatment dosing date; and if both AE onset date and time are missing.

TEAEs will be tabulated by System Organ Class (SOC) and Preferred Term (PT). Summary tables will include number of subjects reporting the AE and as percent of number of subjects dosed by treatment and study overall. The number of AEs will be tabulated in a similar manner. Tables which tabulate the number of TEAEs by severity and relationship to study treatment will also be included.

Serious adverse events (SAEs), if present, will also be listed. Applicable narratives will be included in the CSR.

Frequencies of TEAEs \geq grade 2 in severity (CTCAE version 5), all SAEs, and all AE of Special Interest (AESI) will be tabulated by SOC/TE.

The frequency and severity of clinically significant AEs will be compared descriptively between treatment and historical controls including a previously conducted natural history study at the NIH.

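### SAP 6.3 attributes worsened AEs by onset date and makes no provision for re-enrolment, so an event that worsens at 200 mg can be tabulated under 120 mg or under no treatment

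*SAP*

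**What the plan says.** SAP 6.3 defines the treatment-emergent set by two routes: "A TEAE is defined as an AE that is starting or worsening at the time of or after study drug administration". The next sentence assigns events to doses: "Each TEAE will be attributed to a treatment based on the onset date and time of the AE". It names no date of worsening. An AE with a missing onset date is also declared treatment-emergent.

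The tables depend on this rule. SAP 6.3 states that "only treatment-emergent AEs (TEAEs) will be summarized", with incidence given "as percent of number of subjects dosed by treatment and study overall". The primary endpoint is the frequency of TEAEs of grade 2 or higher, SAEs and AESIs (Protocol 10.2, SAP 2.2). SAP Table 14.3.1.4 presents it by treatment.

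On data capture, Protocol 12.10.7.4 says that for each AE "the investigator will provide the onset date, end date, intensity, treatment required, outcome, seriousness". An AE unresolved at the end of the reporting period stays open as ongoing. Neither document says whether a worsening opens a new record.

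On re-enrolment, the Protocol Précis says "The first three participants received 120 mg S 48168 (ARM210) daily", and the Synopsis adds: "These participants will be provided an opportunity to re-enroll and receive the high dose". Protocol 11.1 gives a re-enrolled participant a new allocation number, and Protocol 12.2 takes an interim medical history. The SAP does not mention re-enrolment, although SAP section 9 states that its analyses agree with the protocol.

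**The concern.** The definition has two ways in, and the attribution rule serves only one. For an AE that starts on drug, the onset date is the date it became treatment-emergent. For an AE that qualifies by worsening, the two dates differ, and the rule uses the wrong one unless the worsening has its own record.

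With one course per person the difference rarely matters, because an event that starts and worsens in the same course is attributed correctly anyway. Re-enrolment changes this: one person can now begin an event at 120 mg and have it worsen at 200 mg.

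At stake is the 200 mg column of the primary-endpoint table, at the dose planned for all remaining participants. Worsening of an existing complaint is plausible in this population. Muscle weakness is the disease itself, raised baseline transaminases are known and have their own AESI threshold (Protocol 12.10.7.7), and fatigue and muscle stiffness are on the expected-AE list (Protocol 12.10.7.2).

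**Working it through.** The plan states no figure on this point to reproduce. The check follows an event through the rule, then sizes one moved subject.

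**Step 1. Where a worsened event lands.** Three readings are open:
- R1: first onset is kept, and both courses sit on one timeline per person.
- R2: first onset is kept, and the courses are separate because the allocation number is new.
- R3: a worsening is entered as a new AE with its own onset.

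| Event | R1 | R2 | R3 |
|---|---|---|---|
| Starts and worsens in the same course | correct dose | correct dose | correct dose |
| Starts in the 120 mg course, worsens at 200 mg | 120 mg | none | 200 mg |
| Starts between courses, worsens at 200 mg | 120 mg | none | 200 mg |
| Starts before any dose, worsens on drug | none | none | dose being taken |

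Under R1, an event between courses is assumed to go to the last treatment taken. R1 and R2 both remove rows 2 and 3 from 200 mg. Only R3 places every event correctly, and the documents neither adopt nor exclude it.

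**Step 2. Who is exposed.** Rows 2 and 3 need two courses, so they concern at most the 3 participants first dosed at 120 mg. Row 4 could concern anyone, but Protocol 12.10.7.4 starts AE reporting after dosing, so most pre-dose complaints should be medical history rather than AEs.

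**Step 3. Missing onset dates.** These events are TEAEs by rule. In a person with two linked courses they cannot be attributed by onset.

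**Step 4. Size of one moved subject, as 100/n points of incidence.**
- 120 mg, n = 3: 100/3 = 33.3 points.
- 200 mg: the documents do not fix the group size, so n is an assumption taken from the target of 8 to 20 completers.
  - Completers counted as courses, 3 of them at 120 mg: n = 8 − 3 = 5 to 20 − 3 = 17, giving 100/5 = 20.0 to 100/17 = 5.9 points.
  - Completers counted as persons, all three re-enrolled: n = 8 to 20, giving 100/8 = 12.5 to 100/20 = 5.0 points.

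**Step 5. When those shifts occur.** An event that began during the 120 mg course is already a 120 mg TEAE, so leaving its worsening there does not raise any-grade incidence. In the primary-endpoint table it adds 33.3 points at 120 mg only under R1, only if the event first meets the grade 2 or higher, SAE or AESI criterion at 200 mg, and only if that person has no other qualifying event at 120 mg. The loss at 200 mg likewise needs a person with no other qualifying event there.

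**The case against.** The strongest reply is that the rule may work as written. SAP 6.3 refers to the onset of the AE, not its first or original onset. Because AE reporting begins after dosing and history is recorded separately, a complaint that worsens on drug would naturally be entered as a new AE dated at the worsening. A new allocation number, fresh consent and an interim history also suggest that the second course is a separate record with one treatment. How worsenings are recorded may be settled in CRF instructions or the medical monitoring plan, which are not available here.

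Much of this stands. It makes the pre-dose case less likely and limits the wrong-dose case to linked records. It does not close the gap. An AE left open from the 120 mg course is followed until resolution or stabilization, even past the reporting window, so it can run into the second course with its first onset date. If records are separate, the event is attributed to no treatment instead of to the wrong dose.

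A reader might go further and infer three things that the documents do not support:
- That worsened events certainly go to the wrong dose or to none. First onset is an inference from the record structure, not the SAP's wording.
- That the safety comparison is biased in favour of 200 mg in general. Only re-enrolled cases move away from 200 mg; pre-dose cases could drop out of either dose. The events stay in the overall counts and by-subject listings, and the plan has no formal dose comparison.
- That any misassigned event shifts 120 mg by 33 points. Step 5 of the working gives the conditions.

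**Conclusion.** The point holds in conditional form. SAP 6.3 admits worsened AEs but gives only an onset rule to attribute them, and it has no provision for a person with two courses. Where an AE keeps its first onset date, an event that worsens at 200 mg after re-enrolment is missing from the 200 mg column of Table 14.3.1.4. It appears under 120 mg if the courses are linked and under no treatment if they are not.

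The exposure is small in people, at most three, but one person is a large share of these groups: 33 points at 120 mg under the stated conditions, and roughly 5 to 20 points at 200 mg. The result rests on two things the documents do not settle, namely whether a worsening opens a new record and how the two allocation numbers relate, and on assumed 200 mg denominators. Since this is a stated rule feeding the primary-endpoint table, and the correction is cheap, it should be fixed before the tables are programmed.

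**What to change.** In SAP 6.3:
- Attribute a TEAE that starts after dosing by its onset date. Attribute a TEAE that qualifies by worsening by the date its CTCAE grade increased, to the course under way then.
- State that a re-enrolled participant's two allocation numbers are linked, and that the baseline for the second course is the grade at re-enrolment.
- Attribute an event with a missing onset date to the course in which it was reported.
- Count a worsened event once per course, at its maximum grade. Without this, an event rising from grade 1 to 2 to 3 could count three times in the event-count tables (14.3.1.2 and 14.3.1.3).

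The date of each grade increase must be captured on the CRF. The cost is a few SAP sentences, a small amount of programming, and a re-check of the AE records of participants already dosed (six when the current protocol was written). No sample size or error rate changes.

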6 SYNOPSIS

Compound:	S 48168 (ARM210)
Clinical Indication:	Ryanodine receptor 1-related congenital myopathy (RYR1 -RM)
Study Phase and Type:	Phase 1 – Safety and Tolerability, pharmacokinetic (PK), and pharmacodynamic/target engagement (PD/TE)
Primary objective:	
To determine safety and tolerability of S 48168 (ARM210) treatment in RYR1-RM affected individuals.
 
Hypothesis: S 48168 (ARM210) treatment will have no safety concerns that limit further development and will be generally well tolerated in RYR1-RM patients.
 
Primary endpoint: Composite safety and tolerability profile (Frequencies of the following: TEAEs \geq grade 2 in severity (CTCAE version 5), all SAEs, and all AESIs).
 
Methods: Safety and tolerability of S 48168 (ARM210) will be determined by monitoring Adverse Events (AEs) over approximately 28 (not to exceed 30) days of treatment via patient interviews, patient diary reviews, physical examinations, echocardiograms, electrocardiograms (ECGs), vital signs, and laboratory safety tests. A reference dataset of AEs/SAEs obtained from a natural history study of RYR1-RM will also be available to assist in interpretation of safety events. The Columbia-Suicide Severity Rating Scale (C-SSRS) will be administered pre- and post-intervention. The frequency and severity of AEs will be compared between treatment and historical controls including a previously conducted natural history study at the NIH.

Exploratory objectives:	
1. To determine PK of a 28 day (not to exceed 30-day) administration of S 48168 (ARM210) in RYR1-RM affected individuals.

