2.2 Endpoints

Primary:

Composite safety and tolerability profile

(Frequencies of the following: TEAEs \geq grade 2 in severity (CTCAE version 5), all SAEs, and all AESIs).

Methods: Safety and tolerability of S 48168 (ARM210) will be determined by monitoring Adverse Events (AEs) over 28 days of treatment via patient interviews, patient diary reviews, physical examinations, echocardiograms, electrocardiograms (ECGs), vital signs, and laboratory safety tests. A reference dataset of AEs/SAEs obtained from a natural history study of RYR1-RM will also be available to assist in interpretation of safety events. The Columbia-Suicide Severity Rating Scale (C-SSRS) will also be administered pre- and post-intervention. The frequency and severity of clinically significant AEs will be compared between treatment and historical controls including a previously conducted natural history study at the NIH.

Exploratory:

1. To determine PK of a 28-day administration of S 48168 (ARM210) in RYR1-RM affected individuals.

Endpoints:

Day 1: AUC_{0 t}, AUC_{0 inf}, C_{max}, T_{max}, and t_{1/2}

Day 28: AUC_{tau}, C_{max}, T_{max}, C_{min}, RAAUC, and RAC_{max}

Secondary PK parameters will include: AUC₀₋₂₄, AUC%extrap, T_{min}, K_{el}, T_{lag}, and Day 13 C_{trough} (associated with Day 14 pre-dose). Additional parameters may be calculated as appropriate.

Methods: Bloods for PK assessments will be drawn at baseline (Day 0, 24h PK), at the study mid-point (day 14 \pm 2 days, trough PK), and at the final study visit (Day 28, 24h PK). Whole blood will be processed, and the plasma fraction stored for batch PK analyses.

2. To explore if S 48168 (ARM210) treatment increases RyR1-calstabin1 binding in skeletal muscle of RYR1-RM affected individuals.

Endpoint: Change from baseline in relative RyR1-calstabin1 binding (AU) and (pending sufficient tissue yield) change from baseline in relative Fluo-4 signal (AU).

Methods: Skeletal muscle tissue will be obtained from participants pre- and post-intervention by needle biopsy. This tissue will be assessed for RyR1-calstabin1

binding by co-immunoprecipitation followed by protein detection. The percentage of Calstabin1 binding to RyR1 pre-dose will be compared to the percentage obtained post-dose in each patient. Pending sufficient tissue yield, muscle membrane preparations may be assessed for changes in calcium permeability (Fluo-4 signal) using a thapsigargin assay.

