The FIH study [REDACTED] that will be the historical control was divided into two parts; part 1 is a randomized placebo-controlled blinded single rising dose escalation study where 5 dose levels were tested ([REDACTED]), and part 2 is a four-panel rising multiple dose study ([REDACTED] [REDACTED] for 14 days of dosing. PK data from [REDACTED] the 240 mg dose level will be utilized for comparisons between healthy subjects and RYR1-RM patients. [REDACTED]

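### The planned comparison of adverse events with a natural history cohort has no common time base and no single event set, so crude frequencies could hide or create an excess risk

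*SAP*

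**What the plan says.** Safety and tolerability are the primary objective of this open-label, non-randomised study. The Protocol synopsis states that "The frequency and severity of AEs will be compared between treatment and historical controls", naming an NIH natural history study among them, and Protocol 12.10 repeats this. SAP 2.2 narrows the events: "The frequency and severity of clinically significant AEs will be compared between treatment and historical controls". SAP 6.3 says these events will be "compared descriptively between treatment and historical controls including a previously conducted natural history study". On the source of the data, SAP 2.2 says only this: "A reference dataset of AEs/SAEs obtained from a natural history study of RYR1-RM will also be available".

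The measures are set out in SAP 6.3: "Summary tables will include number of subjects reporting the AE and as percent of number of subjects dosed by treatment and study overall". Numbers of events are tabulated in the same way, and the general rule in SAP 6 is frequencies and percentages. A TEAE is defined by onset or worsening at or after dosing, with no end date. The AE tables listed in SAP 14.3.1 are by treatment, and none is titled for a natural history group.

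Three periods are given for AEs in the trial: 28 days of treatment (SAP 2.2), the Day 42 assessment that ends participation (Protocol 12.10.7.8), and reporting through 28 days after each dose (Protocol 12.10.7.4).

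**The concern.** The number of events and the percentage of people with at least one event both rise the longer people are watched. A percentage from a six-week trial set beside a percentage from a cohort followed for some other period mixes the effect of the drug with the effect of time. The bias can go either way: a longer comparator hides added risk, and a shorter one creates it.

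The events to be compared are also unsettled. The Protocol compares all AEs. The SAP compares clinically significant AEs and does not define the term. The primary endpoint is TEAEs of grade 2 or higher, SAEs and AESIs. The Protocol's revision history records removal of the phrase clinically significant from the synopsis and the safety assessments section in Amendment 2, so the SAP may simply not have been updated. Even so, SAP 9 states that it is aligned with the Protocol.

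This is the only external comparison that bears on whether patients have more AEs than the disease itself would bring. If the metric is left open, it will be chosen after the open-label data have been seen.

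**Working it through.** **Nothing to reproduce.** Protocol 13.2.1 calls n = 8 sufficient for the safety endpoint but gives no background event rate, comparator size or margin. The figures below are therefore illustrations, not the plan's numbers.

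**Assumptions.** The hazard is constant. Untreated 42-day risk p is 10% or 20%. The length of natural history follow-up is not stated, so 3, 6 and 12 months (91, 182 and 365 days) are shown. The 42 days come from Protocol 12.10.7.8.

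**Step 1: untreated risk over d days** is 1 − (1 − p)^(d/42). **Risk in 42 days with a doubled hazard** is 1 − (1 − p)².

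| | Doubled hazard, 42 days | Untreated, 91 days | Untreated, 182 days | Untreated, 365 days |
|---|---|---|---|---|
| p = 20% | 1 − 0.8² = 36% | 1 − 0.8^2.17 = 38% | 1 − 0.8^4.33 = 62% | 1 − 0.8^8.69 = 86% |
| p = 10% | 1 − 0.9² = 19% | 1 − 0.9^2.17 = 20% | 1 − 0.9^4.33 = 37% | 1 − 0.9^8.69 = 60% |

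A drug that doubles the hazard looks about the same as a 3-month comparator and safer than a 6- or 12-month one.

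**Step 2: where the crude percentages become equal.** This happens when the true hazard ratio is d/42: 91/42 = 2.2, 182/42 = 4.3, 365/42 = 8.7. A larger drug effect than this would still show as an excess.

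**Step 3: the trial's own window.** Keep p = 20% at 42 days and no drug effect. Counting 28 days gives 1 − 0.8^(28/42) = 13.8%. Counting to Day 58 (30 days of dosing plus 28) gives 1 − 0.8^(58/42) = 26.5%. If the natural history data happened to cover 28 days and trial events were counted to Day 58, an inert drug would appear to carry 26.5/13.8 = 1.9 times the risk.

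**Step 4: what a common time base yields.** With 42 days and 30.44 days per month, 8 participants give 8 × 42/30.44 = 11.0 person-months and 20 give 27.6. Two events in 8 participants is 2/11.0 = 0.18 per person-month (exact 95% interval 0.02 to 0.65). With no events, the upper limit of the 95% interval is 0.33 for n = 8 and 0.13 for n = 20. These Poisson limits treat events as independent. Repeat events in one person, or two periods from a re-enrolled person, would make them somewhat too narrow.

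**The case against.** The strongest reply is that little depends on this comparison. The primary endpoint is a frequency within the trial. The natural history data are there to help interpretation, and SAP 6.3 says the comparison is descriptive. Causality assessment, stopping rules and DSMB review do not use it. This stands, and it limits the severity. It does not remove the problem, because unequal windows side by side mislead without any p-value.

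A second reply is that the count-and-percent wording governs the trial's own TEAE tables, while the historical sentence names no metric. That is correct: the plan does not prescribe a crude comparison. But it offers no other measure of frequency. Safety table shells are deferred (SAP 11), yet the list of titles already exists and omits this table.

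Three stronger readings are tempting and not supported.

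- **Drug against drug.** SAP 3 describes the first-in-human volunteer study as the one "that will be the historical control was divided into two parts", and a reader might infer that drug-exposed volunteers enter the AE control group. The same paragraph goes on to PK comparisons, next to redacted text. Protocol 13.2.3 uses healthy-subject data for PK. Treatments C and D appear only in the SAP treatment list and the PK outputs. A PK-only role is the more natural reading.
- **The longer-observed group always shows more AEs.** Step 2 shows that a large enough effect reverses this. Weekly contact and a daily diary may also raise ascertainment in the trial.
- **The natural history study ran on a different clock.** Neither document says how long it followed people or how it collected AEs. A difference is an assumption.

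**Conclusion.** The concern holds as a gap in the time base and the event set of the historical AE comparison. If follow-up in the natural history data differs from the trial's window, crude frequencies can mask a doubling of hazard (36% against 38% to 86% in the 20% example) or suggest a near-doubling where there is none (26.5% against 13.8%). These sizes rest on a constant hazard, assumed background risks and an assumed range of follow-up. The documents supply none of these, so the true bias could be small. The tabulation of the primary endpoint itself is unaffected. The change should be made because it is cheap and concerns the only external comparison for the primary objective, but the trial does not fail without it.

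**What to change.** In SAP 6.3, with matching wording in Protocol 12.10:

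1. Reconcile the trial's AE window across SAP 2.2, Protocol 12.10.7.4 and Protocol 12.10.7.8, and state the one used for this comparison.
2. Report grade 2 or higher AEs and SAEs in both groups as events per person-month with exact confidence intervals, beside the crude percentages. Where AE dates allow, equal-length windows from a defined index date are an alternative. A rate needs only event counts and total follow-up; equal windows need dated events but do not rely on a constant rate.
3. Use the primary endpoint's event set for the comparison as far as the natural history data permit, and drop or define clinically significant. One AESI, plasma Cmax above 35 µg/mL, cannot occur in undosed patients and should be left out of the comparison.
4. Add the table to the SAP 14.3.1 list, with a note on how AEs were collected and graded in each source. A common time base does not correct for more intensive questioning in the trial.
5. Add one clause to SAP 3 saying that the first-in-human study is the PK comparator, if that is the intent.

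Restricting the natural history cohort to people who meet the trial's main entry criteria is optional. It depends on what that dataset records and would make the group smaller.

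The cost is some SAP wording, one table and a little extra analysis of a dataset that the Protocol says will be available. It will not cure imprecision: with 8 to 20 participants the intervals stay wide.
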